6.10 Other Aspects

6.10.1 Changes to the Protocol

Changes to the protocol will be documented in written protocol amendments. Major (i.e., substantial, significant) amendments will be approved by the relevant regulatory authorities and may require submission or notification to the relevant data source institutional review board (IRB)/independent ethics committee (IEC) or regulatory authorities where required by pertinent regulations. In such cases, the amendment will be implemented only after approval or favorable opinion has been obtained.

6.10.2 Study Management

This study will be performed by IQVIA, with guidance, input, review, and approval of Horizon Therapeutics, including development of materials, data management, analysis and reporting.

7 PROTECTION OF HUMAN SUBJECTS

To ensure the quality and integrity of research, this study will be conducted under the guidelines for GVPs (45) and GPPs (38) issued by the ISPE and any applicable national guidelines.

7.1 Independent Ethics Committee/Institutional Review Board

The study protocol will be submitted to the responsible IRB / IEC for its review / approval whenever required by local law. Regulatory authorities will be notified, and approval sought as required by local laws and regulations. Progress reports will be submitted to Ethics Review Boards (ERB) and regulatory authorities as required by local laws and regulations.

When the approval has been granted, the formal procedure of applying for access to and retrieval of patient level health information can be performed to each governing health authority in the respective countries. A prerequisite for approval from an ERB is that the research project is thoroughly described in a study protocol with a clear scientific objective and purpose.

This study is non-interventional, and analysis is based on secondary data use. No identifying data are collected or stored by IQVIA in any of the planned approaches.

IQVIA will adhere to all local and regional laws on data protection and privacy.

8 MANAGEMENT AND REPORTING OF ADVERSE EVENTS/ADVERSE REACTIONS

This study will adhere to the ISPE GPP guidelines (38). This is a non-interventional study design which is based on secondary data use. Expedited reporting of adverse events and Adverse Drug Reactions at the individual case level is not required.

9 PLANS FOR DISSEMINATING AND COMMUNICATING STUDY RESULTS

9.1 Progress Report

The progress reports will be produced annually for inclusion in the scheduled PSUR for the product. Progress reports will contain descriptive analysis of the cohorts within each country, including number of patients treated with the study drug where possible (data applications permitting), in order to monitor the feasibility of the study. Multiple extractions are planned. The number of extraction and dates may vary by country due to differences in data governance and product launch date. Examination of aggregate cohort characteristics, drug utilization, and AESI will be presented in final report.

9.2 Annual/Interim Analyses and Reporting

Not Applicable.

9.3 Final Analyses and Reporting

A final study report will be generated after all data collection is complete, including up to 57 months of study period (Table 1). The final study report will be submitted as a standalone procedure to the competent authorities 12 months after the availability of final analytical data set. The final report will encompass all planned analyses, including a description of the complete study population, as described above and in the SAP.

In accordance with the 2010 EU pharmacovigilance legislation (Articles 10 or 10a of Regulation (EC) No 726/2004; Articles 21a or 22a of Directive 2001/83/EC) (46,47), information about this PASS will be entered into the publicly available EU PAS register (<http://www.encepp.eu/encepp/studiesDatabase.jsp>). The study protocol will be entered into the register before the start of data collection. Updates to the study protocol in case of substantial amendments, progress reports where applicable, and the final study report will also be entered in the register.

9.4 Publications

Study findings will be published in a peer reviewed journal.

Any publication of the results from this study must be consistent with the Horizon Therapeutics publication policy and guided by the Uniform Requirements for Manuscripts Submitted to Biomedical Journals: Writing and Editing for Biomedical Publication of the International Committee of Medical Journal Editors, updated April 2010 (48). The rights of the investigator and of the Horizon Therapeutics with regard to publication of the results of this study are described in the investigator contract.

All reporting will be consistent with the STROBE Initiative checklist for cohort studies (37).

In order to allow competent authorities to review in advance the results and interpretations to be published, the MAH should communicate to the Agency and the competent authorities of the Member States in which the product is authorized the final manuscript of the article within 2 weeks after first acceptance for publication.

ANNEX 1. LIST OF STAND-ALONE DOCUMENTS

	Document reference number	Date	Title
1	<Number>	<DD Month YYYY>	<Text>
2	<Number>	<DD Month YYYY>	<Text>
...	<Number>	<DD Month YYYY>	<Text>

ANNEX 2. ENCEPP CHECKLIST FOR STUDY PROTOCOLS.

ENCePP Checklist for Study Protocols (Revision 4)

Adopted by the ENCePP Steering Group on 15/10/2018

Study title: A real-world observational study of treatment patterns and outcomes for patients with Neuromyelitis optica spectrum disorders (NMOSD) treated with inebilizumab (UPLIZNA) in Europe
EU PAS Register® number: Study not yet registered
Study reference number (if applicable): N/A

Section 1: Milestones	Yes	No	N/A	Section Number
1.1 Does the protocol specify timelines for				
1.1.1 Start of data collection ²				3.0
1.1.2 End of data collection ³				
1.1.3 Progress report(s)				
1.1.4 Interim report(s)				
1.1.5 Registration in the EU PAS Register®				
1.1.6 Final report of study results				

Comments:

--

Section 2: Research question	Yes	No	N/A	Section Number
2.1 Does the formulation of the research question and objectives clearly explain:				5
2.1.1 Why the study is conducted? (eg, to address an important public health concern, a risk identified in the risk management plan, an emerging safety issue)				4.2
2.1.2 The objective(s) of the study?				5
2.1.3 The target population? (ie, population or subgroup to whom the study results are intended to be generalised)				5
2.1.4 Which hypothesis(-es) is (are) to be tested?				
2.1.5 If applicable, that there is no a priori hypothesis?				6.5

² Date from which information on the first study is first recorded in the study dataset or, in the case of secondary use of data, the date from which data extraction starts.

³ Date from which the analytical dataset is completely available.

Comments:

--

Section 3: Study design		Yes	No	N/A	Section Number
3.1	Is the study design described? (eg, cohort, case-control, cross-sectional, other design)				6.1
3.2	Does the protocol specify whether the study is based on primary, secondary or combined data collection?				6.1
3.3	Does the protocol specify measures of occurrence? (eg., rate, risk, prevalence)				6.7.2
3.4	Does the protocol specify measure(s) of association? (eg, risk, odds ratio, excess risk, rate ratio, hazard ratio, risk/rate difference, number needed to harm (NNH))				
3.5	Does the protocol describe the approach for the collection and reporting of adverse events/adverse reactions? (eg, adverse events that will not be collected in case of primary data collection)				

Comments:

--

Section 4: Source and study populations		Yes	No	N/A	Section Number
4.1	Is the source population described?				6.1
4.2	Is the planned study population defined in terms of:				6.1
	4.2.1 Study time period				6.1
	4.2.2 Age and sex				6.4
	4.2.3 Country of origin				6.1
	4.2.4 Disease/indication				6.3
	4.2.5 Duration of follow-up				6.1
4.3	Does the protocol define how the study population will be sampled from the source population? (eg, event or inclusion/exclusion criteria)				6.2

Comments:

--

Section 5: Exposure definition and measurement		Yes	No	N/A	Section Number
5.1	Does the protocol describe how the study exposure is defined and measured? (eg, operational details for defining and categorising exposure, measurement of dose and duration of drug exposure)				6.3.1 6.3.3

Section 5: Exposure definition and measurement	Yes	No	N/A	Section Number
5.2 Does the protocol address the validity of the exposure measurement? (eg, precision, accuracy, use of validation sub-study)				6.3.1 6.9
5.3 Is exposure categorised according to time windows?				6.3.2
5.4 Is intensity of exposure addressed? (eg, dose, duration)				6.3.2
5.5 Is exposure categorised based on biological mechanism of action and taking into account the pharmacokinetics and pharmacodynamics of the drug?				
5.6 Is (are) (an) appropriate comparator(s) identified?				

Comments:

Section 6: Outcome definition and measurement	Yes	No	N/A	Section Number
6.1 Does the protocol specify the primary and secondary (if applicable) outcome(s) to be investigated?				
6.2 Does the protocol describe how the outcomes are defined and measured?				6.3 Annex 3
6.3 Does the protocol address the validity of outcome measurement? (eg, precision, accuracy, sensitivity, specificity, positive predictive value, use of validation sub-study)				6.9
6.4 Does the protocol describe specific outcomes relevant for Health Technology Assessment? (eg, HRQoL, QALYs, DALYS, health care services utilisation, burden of disease or treatment, compliance, disease management)				

Comments:

Please note the study is descriptive by nature, however we considered the safety events as the outcome.

Section 7: Bias	Yes	No	N/A	Section Number
7.1 Does the protocol address ways to measure confounding? (eg, confounding by indication)				
7.2 Does the protocol address selection bias? (eg, healthy user/adherer bias)				6.2 6.9
7.3 Does the protocol address information bias? (eg, misclassification of exposure and outcomes, time-related bias)				6.9

Comments:

--

Section 8: Effect measure modification	Yes	No	N/A	Section Number
8.1 Does the protocol address effect modifiers? (eg, collection of data on known effect modifiers, sub-group analyses, anticipated direction of effect)				6.1

Comments:

--

Section 9: Data sources	Yes	No	N/A	Section Number
9.1 Does the protocol describe the data source(s) used in the study for the ascertainment of:				
9.1.1 Exposure? (eg, pharmacy dispensing, general practice prescribing, claims data, self-report, face-to-face interview)				6.3.1 6.3.3
9.1.2 Outcomes? (eg, clinical records, laboratory markers or values, claims data, self-report, patient interview including scales and questionnaires, vital statistics)				6.3.4
9.1.3 Covariates and other characteristics?				6.3.2
9.2 Does the protocol describe the information available from the data source(s) on:				
9.2.1 Exposure? (eg, date of dispensing, drug quantity, dose, number of days of supply prescription, daily dosage, prescriber)				8.4.1 8.4.2 8.4.3
9.2.2 Outcomes? (eg, date of occurrence, multiple event, severity measures related to event)				8.4.1 8.4.2 8.4.3
9.2.3 Covariates and other characteristics? (eg, age, sex, clinical and drug use history, co-morbidity, co-medications, lifestyle)				8.4.1 8.4.2 8.4.3
9.3 Is a coding system described for:				
9.3.1 Exposure? (eg, WHO Drug Dictionary, Anatomical Therapeutic Chemical (ATC) Classification System)				8.3.1
9.3.2 Outcomes? (eg, International Classification of Diseases (ICD), Medical Dictionary for Regulatory Activities)				Annex 3
9.3.3 Covariates and other characteristics?				6.3.2 Annex 3
9.4 Is a linkage method between data sources described? (eg, based on a unique identifier or other)				6.4.1 6.4.2

Comments:

--

Section 10: Analysis plan	Yes	No	N/A	Section Number
10.1 Are the statistical methods and the reason for their choice described?				6.7.2
10.2 Is study size and/or statistical precision estimated?				6.5
10.3 Are descriptive analyses included?				6.7.2
10.4 Are stratified analyses included?				6.7.2
10.5 Does the plan describe methods for analytic control of confounding?				
10.6 Does the plan describe methods for analytic control of outcome misclassification?				
10.7 Does the plan describe methods for handling missing data?				
10.8 Are relevant sensitivity analyses described?				

Comments:

Section 11: Data management and quality control	Yes	No	N/A	Section Number
11.1 Does the protocol provide information on data storage? (e.g., software and IT environment, database maintenance and anti-fraud protection, archiving)				6.8
11.2 Are methods of quality assurance described?				6.8
11.3 Is there a system in place for independent review of study results?				9.4

Comments:

Section 12: Limitations	Yes	No	N/A	Section Number
12.1 Does the protocol discuss the impact on the study results of:				6.9
12.1.1 Selection bias?				
12.1.2 Information bias?				
12.1.3 Residual/unmeasured confounding? (e.g., anticipated direction and magnitude of such biases, validation sub-study, use of validation and external data, analytical methods).				
12.2 Does the protocol discuss study feasibility? (e.g., study size, anticipated exposure uptake, duration of follow-up in a cohort study, patient recruitment, precision of the estimates)				6.4

Comments:

Section 13: Ethical/data protection issues	Yes	No	N/A	Section Number
13.1 Have requirements of Ethics Committee/ Institutional Review Board been described?				7.1
13.2 Has any outcome of an ethical review procedure been addressed?				
13.3 Have data protection requirements been described?				7.1

Comments:

Section 14: Amendments and deviations	Yes	No	N/A	Section Number
14.1 Does the protocol include a section to document amendments and deviations?				2.0

Comments:

Section 15: Plans for communication of study results	Yes	No	N/A	Section Number
15.1 Are plans described for communicating study results (eg, to regulatory authorities)?				9
15.2 Are plans described for disseminating study results externally, including publication?				9.4

Comments:

Name of the main author of the protocol: ██████████ _____

Date: 28 February 2023

Signature: _____

ANNEX 3. ADDITIONAL INFORMATION

Table 6 List of Comorbidities

Comorbidities	Diagnosis ICD-9-CM Codes*	Diagnosis ICD-10-CM Codes*
Coronary heart disease	410.xx, 411.xx, 412, 413.x, 414.xx	I21.xx, I24.x, I25.2, I20.x, I25.xxx
Heart failure	398.91, 402.01, 402.11, 402.91, 404.01, 404.03, 404.11, 404.13, 404.91, 404.93, 428.xx	I09.81, I11.0, I13.0, I13.2, I50.xx
Cerebrovascular disease	430, 431, 432.x, 433.xx, 434.xx, 435.x, 436, 437.0, 437.1, 437.8, 437.9, 438.xx, 997.02	I60.9, I61.9, I62.xx, I63.xx, I65.xx, I66.xx, G45 [excl. G45.4], I67.84, I67.2, I67.81, I67.82, I67.89, I67.9, I69.8, I69.9x, I97.81, I97.82
Lung disease	493.00-493.02, 493.10-493.12, 493.20-493.22, 493.81, 493.82, 493.90-493.92, 491.0, 491.1, 491.20-491.22, 491.8, 491.9, 492.0, 492.8, 496, 490, 494.0, 494.1, 495.0-495.9, 500, 501, 502, 503, 504, 505, 506.4	J45.2x-J45.5x, J45.9xx, J41.x, J42, J43.x, J44.x, J60, J61, J62.x, J63.x, J64, J65, J66.x, J67.x, J68.4
Renal disease	403.01, 403.11, 403.91, 404.02, 404.03, 404.12, 404.13, 404.92, 404.93, 582.x, 583.0-583.7, 585.x, 586, 588.xx, V42.0, V45.1x, V56.x	I12.0, I13.11, I13.2, N03.x, N05.9, N05.2, N05.5, N17.1, N18.x, N19, N25.xx, Z94.0, Z99.2, Z91.15, Z49.xx
Rheumatic disease	446.5, 710.0-710.4, 714.0-714.2, 714.81, 725	M31.5, M31.6, M32.xx, M34.xx, M35.0x, M33.xx, M05.xxx, M35.3
Diabetes	249.xx, 250.xx, 357.2, 362.0x, 366.41, 648.0, E932.3, V58.67	E08.xx, E09.xx, E10.x, E11.xx, E13.xx, O24 [excl. O24.4], Z79.4
Hypertension	401.x, 402.xx, 403.xx, 404.xx, 405.xx	I10, I11.x, I12.x, I13.xx, I15.x, I16.x
Malignancy	140.x-171.x, 174.x-195.x, 200.x- 207.x, 209.0x - 209.3x, 173.00, 173.09, 173.10, 173.19, 173.20, 173.29, 173.30, 173.39, 173.40, 173.49, 173.50, 173.59, 173.60, 173.69, 173.70, 173.79, 173.80, 173.89, 173.90, 173.99, 796.76, 795.06, 795.16	C00.x-C43.x, C4A.x, C45.x- C96.x, C44.00, C44.09, C44.10x, C44.19x, C44.20x, C44.29x, C44.30x, C44.39x, C44.40, C44.49, C44.50x, C44.59x, C44.60x, C44.69x, C44.70x, C44.79x, C44.80x, C44.89, C44.90, C44.99, R85.614, R87.614, R87.624
Osteoporosis	733.0x, 733.1x	M80.xxxx, M81.x
Anxiety	300.2x, 300.0x, 300.3	F40.xxx, F41.x, F42.x
Depression	296.21, 296.22, 296.23, 296.26, 296.31, 296.32, 296.33, 296.36	F32.x, F33.xx
Skin ulcers/cellulitis	681.00, 681.10, 681.9, 682.x, 707.xx	L03.01x, L03.03x, L03.11x, L03.21x, L03.31x, L03.81x, L03.90, L89.x, L97.x

Comorbidities	Diagnosis ICD-9-CM Codes*	Diagnosis ICD-10-CM Codes*
Renal transplantation	55.69, V42.0	Z94.0
Infections	Available upon request	Available upon request

Abbreviations: ICD-9/ICD-10, 9th/10th Revision of International Classification of Diseases; CM, Clinical Modification
*ICD-X-CM codes will be translated into local ICD-X codes and provided in SAP

Table 7 NMOSD-Associated Conditions

NMOSD-associated Conditions	Diagnosis ICD-9-CM Codes*	Diagnosis ICD-10-CM Codes*
Hypothyroidism	244.x	E89.0, E03.2, E03.8, E03.9
Pernicious anemia	281.0, 281.1	D51.x
Ulcerative colitis	556.x [excl. 556.2 and 556.3]	K51.xx [excl. K51.2x and K51.3x]
Myasthenia gravis	358.0x	G70.0x
Idiopathic thrombocytopenic purpura	446.6	M31.1
Hemiplegia/paraplegia	334.1, 342.x, 343.x, 344.0x-344.6x, 344.9	G11.4, G81.xx, G80.x, G83.0, G83.1x, G83.2x, G83.3x, G83.4, G83.9, G82.xx
Bladder dysfunction	788.30, 788.31, 788.33, 788.34, 788.36, 788.37, 788.39-788.43, 596.xx	N30.xx, N31.x, N32.xx, N33
Neuropathic pain	353.x, 354.x, 355.x, 356.x, 357.x, 250.6, 729.2, 782	E08.40-E08.42, E09.40, E09.42, E10.40-E10.42, E11.40-E11.42, E13.40-E13.42, G50.0, G50.1, G54.x, G55.x, G56.x, G57.x, G58.x, G60.x, G61.x, G62.x, G63, G64, G65.x, G90.5x, M05.5x, M79.2, M54.1, R20
Antiphospholipid syndrome	289.81	D68.61
Sarcoidosis	135	D86.xx
Scleroderma	357.4, 359.6, 517.2, 701.0, 710.1	M34.xx, L90.0, L94.0, L94.1, L94.3
Sjogren's syndrome	710.2	M35.0x
Systemic lupus erythematosus	710	M32.xx
Dorsalgia	724.5	M54
Disorders of lipoprotein metabolism and other lipidemias	272.0, 272.1, 272.2, 272.3, 272.4, 272.5, 272.9	E78
Other acute disseminated demyelination	341.9	G36.9
Disorders of refraction and accommodation	367	H52
Visual disturbances	368	H53
Disturbances of skin sensation	782	R20
Somatoform disorders	300.81	F45
Other dorsopathies, not elsewhere classified	723.2, 723.3, 723.8, 723.9	M53

NMOSD-associated Conditions	Diagnosis ICD-9-CM Codes*	Diagnosis ICD-10-CM Codes*
-----------------------------	------------------------------	-------------------------------

Abbreviations: ICD-9/ICD-10, 9th/10th Revision of International Classification of Diseases; CM, Clinical Modification; NMOSD, Neuromyelitis optica spectrum disorder

*ICD-X-CM codes will be translated into local ICD-X codes and provided in SAP

Table 8 Acute Treatments

Name of Agent	Description	Coding
Intravenous Corticosteroids*	H02 - Corticosteroids for systemic use	ATC
Intravenous Immunoglobulin (IVIG)*	J06B - Immunoglobulins	ATC
	8-810.w Human immunoglobulin, polyvalent	OPS
Plasma Exchange (PLEX)	6A550Z3 - Pheresis of Plasma, Single	ICD-10-PCS
	6A551Z3 - Pheresis of Plasma, Multiple	ICD-10-PCS
	8-820 Therapeutic plasmapheresis	OPS

Abbreviations: ATC, Anatomical therapeutic chemical; ICD-10: 10th Revision of International Classification of Diseases; OPS, operation and procedure classification system, PCS, Procedure Coding System

* Only intravenous administrations

Table 9 NMOSD Maintenance Therapies

Name of Agent	Description	Coding
1. Oral Steroids	H02 - Corticosteroids for systemic use	ATC
2. Immunosuppressive therapies		
a. Azathioprine	L04AX01	ATC
b. Mitoxantrone	L01DB07	ATC
c. Mycophenolate Mofetil	L04AA06	ATC
d. Methotrexate	L01BA01; L04AX03	ATC
e. Cyclophosphamide	L01AA01	ATC
3. B-Cell Targeting Therapy (anti-CD20)		
a. Ocrelizumab	L04AA36 /L04AG08 from 2024	ATC
	6-00a.e Atezolizumab, parenteral	OPS
b. Ofatumumab	L04AA52/ L04AG12 from 2024	ATC
	6-006.4 Ofatumumab, parenteral	OPS
c. Rituximab	L01FA01	ATC
	6-001.h Rituximab, intravenously	OPS
	6-001.j Rituximab, subcutaneous	
4. Tocilizumab	L04AC07	ATC
	6-005.m Tocilizumab, intravenously	OPS
	6-005.n 8 Tocilizumab, subcutaneous	
5. Eculizumab	L04AA25/L04AJ01 from 2024	ATC
	6-003.h Eculizumab, parenteral	OPS
6. Satralizumab	L04AC19	ATC

Abbreviations: ATC, Anatomical therapeutic chemical; NMOSD, Neuromyelitis optica spectrum disorder; OPS, operation and procedure classification system

Table 10 Other Immunosuppressive Drugs of Interest

Name of Agent	Description	Coding
1. Interferon beta-1a and 1b	L03AB07; L03AB08	ATC
2. Dimethyl-fumarate	L04AX07; L04AX09	ATC
3. Alemtuzumab	L04AA34/L04AG06 from 2024	ATC
	6-001.0 Alemtuzumab, parenteral	OPS
4. Fingolimod	L04AA27/L04AE01 from 2024	ATC
5. Natalizumab	L04AA23/L04AG03 from 2024	ATC
	6-003.f Natalizumab, parenteral	OPS
6. Glatiramer acetate	L03AX13	ATC
7. Peginterferon beta-1a	L03AB13	ATC
8. Teriflunomide	L04AA31/L04AK02 from 2024	ATC
9. Bortezomib	L01XG01	ATC
	6-001.9 Bortezomib, parenteral	OPS
10. Cladribine	L01BB04; L04AA40	ATC
	6-00a.4 Cladribine, oral	OPS
11. Daclizumab	L04AC0	ATC
	6-009.9 Daclizumab, parenteral	OPS
12. Ozanimod	L04AA38/L04AE02 from 2024	ATC
13. Siponimod	L04AA42/L04AE03 from 2024	ATC
14. Tacrolimus	L04AD02	ATC

Abbreviations: ATC, Anatomical therapeutic chemical; OPS: operation and procedure classification system

Table 11 Pain Medication

Name of Agent	Description	Coding
1. Anti-inflammatory and antirheumatic drugs	M01	ATC
2. Topical products for joint and muscular pain	M02	ATC
3. Muscle relaxants	M03	ATC
4. Anesthetic drugs	N01	ATC
5. Analgesics	N02	ATC

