6.4.4 Italy

The Italian Multiple Sclerosis & Related Disorders Register (*Registro Italiano Sclerosi Multipla e Patologie Correlate* [RISM]) was officially established in 2015. As of February 2023, the register was actively covering 133 MS centers, corresponding to a total of 80,353 patients, of which 273 are diagnosed with NMOSD. Since July 2022, the

register comprises a module for the collection of information on NMOSD, and has projects dedicated to NMOSD patients (22). Nonetheless, data on NMOSD patients were collected previous to 2022, without a specific module implemented. The data are collected from participating centers through a web-based system developed for the study, available at the IMS&RD website. Data are collected from accrual to exit of database, which may occur at date of death, when patient moves to a center outside of the covered network or withdraws their consent to participate. The data are centrally monitored to ensure quality of data, completeness, accuracy, and consistence (23). Requests to access the data are evaluated by the Scientific Committee, composed by clinicians, methodologists, representatives of MS centers, and of the Italian Neurological Society (23).

To ensure the collection of sufficient data for the clinical characterization of the single patient mandatory variables collected by the register include patient identification, demographics, vital status, disease onset date, diagnosis date, relapses, treatments and severe adverse events. This minimum dataset may be completed with an extension to optional information on family history, comorbidities, laboratory tests and MRI. Furthermore, the register has data on patient's unique personal identifier, to avoid inclusion of the same patient by more than 1 center. Diagnosis information is available and captured with ICD-9-CM coding system.

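### In several rows of Tables 6 and 7 the ICD-9 and ICD-10 code lists differ in breadth or content, so one baseline label is defined differently for Italy and for the ICD-10 sources

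*Protocol*

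**What the plan says.** Section 6.3.2 assesses comorbidities and NMOSD-associated conditions by the presence of ICD-9 or ICD-10 codes, listed in Annex 3 (Tables 6 and 7). Each row has one label and two parallel lists. A footnote says that the listed codes will be translated into local codes in the SAP.

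The sources do not share a coding system. For the Italian register, section 6.4.4 states: "Diagnosis information is available and captured with ICD-9-CM coding system". French hospital diagnoses are in ICD-10 (section 6.4.1) and German claims are in ICD-10-GM (section 6.4.2). Section 6.7.1 has all descriptive analyses done by country or data source.

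For cerebrovascular disease the ICD-9 cell is "430, 431, 432.x, 433.xx, 434.xx, 435.x, 436, 437.0, 437.1, 437.8, 437.9, 438.xx, 997.02". The ICD-10 cell starts "I60.9, I61.9, I62.xx, I63.xx, I65.xx, I66.xx" and ends "I69.8, I69.9x, I97.81, I97.82".

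**The concern.** A table that sets Italy beside France and Germany invites the reader to compare patients. That works only if the two columns of a row describe the same condition at the same breadth. Where they do not, the same patient could count under the label in one country and not in another.

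The mismatch does not run in one direction. Some rows are narrower in ICD-10, some are narrower in ICD-9, and one differs both ways, so a single caveat about undercounting would not cover it. If baseline percentages are also pooled, as the precision argument in section 6.5 envisages, a pooled figure would mix two definitions.

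**Working it through.** There is no sample-size or power figure to reproduce. The check sets the two columns side by side, expands the ranges, and compares them with Table 12 where the same condition appears. Malignancy and dorsalgia can be shown from the protocol's own tables. The other rows also rely on the standard meaning of the ICD codes.

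1. **Malignancy (Table 6).** ICD-9 lists "140.x-171.x, 174.x-195.x, 200.x- 207.x, 209.0x - 209.3x" plus selected 173 codes. Of categories 140 to 209, this leaves out 172, 196, 197, 198, 199 and 208. ICD-10 runs C00 to C43 and C45 to C96, plus C4A and selected C44 codes, and leaves out no category of C00 to C96. Melanoma (172 against C43) and secondary or unspecified-site cancers (196-199 against C77-C80) therefore count only in ICD-10 data. Table 12 uses the unbroken 140-209 and C00-C96. *ICD-9 is narrower.*

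2. **Cerebrovascular disease (Table 6).** ICD-9 takes 430, 431 and 438.xx whole. ICD-10 takes only I60.9, I61.9, I69.8 and I69.9x from the corresponding categories. The same cell writes I62, I63, I65 and I66 with wildcards, so the table's own notation shows that I60.9 and I61.9 are single codes. I60.0 to I60.8 and the site-specific I61 codes are lost. *ICD-10 is narrower.*

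3. **Lung disease (Table 6).** ICD-9 includes 490, 494.0 and 494.1. The ICD-10 list contains J41 to J45 codes but neither J40 nor J47. *ICD-10 is narrower.*

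4. **Rheumatic disease (Table 6).** The ICD-9 cell ends "714.0-714.2, 714.81, 725". Its rheumatoid arthritis codes face M05 only; M06 is absent. *ICD-10 is narrower.*

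5. **Depression (Table 6).** The ICD-9 list starts "296.21, 296.22, 296.23, 296.26" and repeats the pattern for 296.3x, giving eight codes with final digit 1, 2, 3 or 6. ICD-10 takes all of F32 and F33. *ICD-9 is narrower.*

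6. **Bladder dysfunction (Table 7).** ICD-9 lists 596.xx and a set of 788.3x-788.4x symptom codes. ICD-10 lists "N30.xx, N31.x, N32.xx, N33". The incontinence and frequency codes have no ICD-10 counterpart, and N30 (cystitis) appears only in ICD-10. *The row differs both ways.*

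7. **Dorsalgia (Table 7).** ICD-9 724.5 faces the whole of M54. Table 12 pairs the same 724.5 with M54.9. Table 7 also gives M54.1 to neuropathic pain. *ICD-9 is narrower.*

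**Reach.** Table 6 has 15 rows, of which five are affected; Table 7 has 21, of which two are affected. That is 7 of 15 + 21 = 36 rows. As a rough guide to where ICD-9 applies, Italy is 39,908,080 of 110,687,896 in Table 4, or 36% of the source population. This is a share of the population covered, not of inebilizumab users.

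**Does translation repair it?** A local version of I60.9 is still I60.9, and N30 remains N30. Faithful translation of two unequal lists leaves them unequal.

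**The case against.** The strongest reply is that this belongs to the SAP. Section 6.3.2 allows the characterization variables to be refined according to database availability and defers detailed operational definitions and local codes to the SAP, which is not at hand. The SAP could re-match the columns. But the protocol has already stated the lists, and its footnotes promise translation only; nothing commits to matching them.

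A second reply is that other causes of country difference exist and are partly disclosed. Comorbidities are optional data in the Italian register (section 6.4.4). Section 6.9 already mentions varying ICD-10 coding practice and misclassification of associated conditions. No between-country test is planned. This stands, and it means that the code lists explain only part of any difference. It does not cover a mismatch that the protocol itself creates.

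Several stronger readings are tempting but not supported:

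- A reader might infer that the paired columns describe different diseases throughout. In the cerebrovascular and rheumatic rows the ICD-10 list is a narrower part of the same disease group. I62, I63, I65 and I66 are complete, so no large loss of patients is shown.
- A reader might infer that bladder dysfunction would mainly mean cystitis in the ICD-10 countries and incontinence in Italy. The ICD-10 list also has N31 to N33, the ICD-9 list also has 596.xx, and nothing gives their relative frequency.
- A reader might try to put a percentage on N30. Section 4.1 gives the female share (70%-90%), but the documents contain no frequency of coded cystitis. Any such figure could apply only to the ICD-10 sources, not to the whole cohort.
- The bare 710 for lupus and 782 for skin sensation may simply have lost a zero. They need checking but are not counted here.

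**Conclusion.** The point holds as a mismatch in breadth or content in at least seven rows of Tables 6 and 7. It rests on the lists being applied as written, with ICD-9-CM in Italy and ICD-10 in France and Germany. For the Netherlands the ICD revision of the hospital data is not named, and for Spain only a feasibility footnote refers to an ICD-10 code, so the argument does not depend on those two.

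The consequence is limited to the descriptive baseline results of Objective 1, where part of any difference between Italy and the ICD-10 sources in these rows would be produced by the lists. Its size in patients cannot be given from the documents. The safety outcomes have their own lists in Table 12, and the Charlson index is to have its own list in the SAP. The point is minor but cheap to correct.

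**What to change.** Before local translation, define each row once in clinical terms and match the two columns:

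- **Malignancy:** add 172, 196-199 and 208 to ICD-9 so that it matches C00-C96. The selected 173 and C44 codes already run parallel.
- **Cerebrovascular disease:** use I60.x, I61.x and I69.x.
- **Lung disease:** add J40 and J47.
- **Rheumatic disease:** add M06.
- **Depression:** widen the ICD-9 codes to the breadth of F32 and F33.
- **Bladder dysfunction:** remove N30 and add ICD-10 counterparts only for the 788.x codes listed (N39.4, R32, R35). Do not add N39.3 unless the ICD-9 side is widened too, because 788.32 is not listed there. State that symptom codes have little or no coverage in the German claims (section 6.4.2), so this row will remain weak there.
- **Dorsalgia:** align with the pairing in Table 12.

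The cost is a code-list edit in Annex 3, carried into the SAP before programming starts. It needs no new data and changes neither the patients included nor the timelines.
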